All subjects will be hospitalized for intensive monitoring for 48 hours post tarlatamab infusion during all cycle 1 doses. Hospitalization is not required for cycle 2 unless a subject experiences grade 2 or higher CRS or neurological events in cycle 1 (minimum of 24 hours hospitalization required post tarlatamab infusion on cycle 2 day 1 if grade 2 or higher CRS or neurological events are noted in cycle 1). The subjects may be discharged after this period if there are no signs and symptoms of CRS or other acute

toxicities. If subjects are not hospitalized during cycle 2, subjects will be observed for 8 hours post tarlatamab infusion.

Routine radiological imaging (computed tomography [CT]/magnetic resonance imaging [MRI]) and tumor burden assessments will be performed as outlined in the Schedule of activities. Assessment of disease response will be determined based on RECIST 1.1 per PCWG3 guidelines (Sections 11.8 and 11.9). To further assess the risk of delayed adverse events, the subject must return for safety follow-up (SFU) visit approximately 60 (+5) days after the last dose of tarlatamab.

Long-term follow-up will be conducted every 3 months up to 3 years from the first dose of tarlatamab for all subjects who have not withdrawn consent by clinic visit, telephone or chart review to assess for survival and/or the commencement of subsequent cancer therapy.

For a full list of study procedures, including the timing of each procedure, please refer to Section 8.2 and the Schedule of Activities in Section 1.3.

Statistical Considerations

All subjects who are enrolled and receive at least 1 dose of tarlatamab will be included in the analysis, unless otherwise specified.

The primary analysis will occur when target enrollment is complete and each subject either completes at least 6 months on study or withdraws from the study. The final analysis will be performed after the last subject has had an opportunity to complete the corresponding end of treatment visit/procedures.

Descriptive statistics will be provided for selected demographics, safety, pharmacokinetic, efficacy data by dose, dose schedule, and time as appropriate.

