4.1 Overall Design

This is an open label phase 1b study evaluating tarlatamab monotherapy.

[figure not shown]
Tarlatamab will be administered as a short-term IV infusion Q2W (with step dosing) in a 28-day cycle as monotherapy therapy in subjects with de novo or treatment-emergent NEPC.

The study will consist of 2 parts: dose exploration (Part 1) and dose expansion (Part 2).

Dose Exploration (Part 1)

The dose exploration part of the study will enroll up to 20 subjects with relapsed/refractory (RR) NEPC. At the time of initiation of the study, the starting dose will be the highest dose deemed safe and tolerable in the ongoing phase 1 trial of tarlatamab in subjects with small cell lung cancer (Note: based on emerging safety data

from Study 20160323, the starting dose may be lower than the highest dose deemed safe and tolerable). The planned highest dose in this study is not anticipated to exceed the maximum tolerated dose (MTD) as established in the ongoing Study 20160323. Based on results from study 20160323 in small cell lung cancer, the doses that may be explored in this study are presented in [Table 4-1](#).

Due to its known mechanism of action, subjects are at an increased risk for first dose effects (eg, CRS with associated manifestations and any other potentially evolving and unknown first dose effects) following the initial infusion of tarlatamab. To mitigate these risks, a step dosing approach will be implemented. One of the following step dosing approaches will be utilized as the initial dosing schedule based on emerging data and the dosing schedule associated with the highest dose deemed safe and tolerable from the ongoing first-in-human (FIH) study (Note: based on emerging safety data from Study 20160323, the starting dose may be lower than the highest dose deemed safe and tolerable).

- Single-step dosing involving a run-in dose on day 1, followed by a step dose on day 8 (equal to the target dose) and the target dose on day 15 then Q2W.

Based on emerging safety, pharmacokinetic and pharmacodynamic data from this study as well as the ongoing FIH study (20160323) and the recommendations of the DLRT, multiple or parallel dosing cohorts may also be opened simultaneously to assess any of the step-dosing strategies as described above.

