8.1.3 Safety Follow-up

Upon permanent discontinuation from the study treatment for any reason to further assess the risk of delayed adverse events, an SFU visit will be performed approximately **60 (+5)** days after the end of the last dose of tarlatamab.

The study procedures to be completed during the SFU period are designated in the Schedule of Activities ([Table 1-2](#)).

The following procedures will be completed for patients who have not started subsequent anti-cancer therapy. Additional tests can be conducted at the discretion of the investigator.

- Clinical evaluation
 - Physical examination as per standard of care (including medical/surgical history). Physical examination findings should be recorded on the appropriate eCRF.
 - ECOG performance status
 - Weight
- Vital signs (ie, blood pressure, heart rate, respiratory rate, and temperature)
- Pulse oximetry
- Serious adverse event reporting
- Adverse event reporting
- Documentation of concomitant and rescue medications

This information may be collected by clinic visit, telephone or chart review.

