8.2.4.1 Time Period and Frequency for Collecting and Reporting Safety Event Information

8.2.4.1.1 Adverse Events

The adverse event grading scale to be used for this study will be the CTCAE and is described in Section 11.4.

The investigator is responsible for ensuring that all adverse events observed by the investigator or reported by the subject that occur after first dose of investigational product through the **safety follow-up visit or 60 days after the last day of the dosing interval of investigational product(s) or noninvestigational product(s)/auxiliary medicinal product(s), whichever is later**, are reported using the Events CRF.

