After the escalation phase is completed, final DLT rates at each dose level will be estimated by isotonic regression (Ji et al, 2010). The weighted least squares regression model will assume monotonic non-decreasing DLT rates with increasing dose and use the empirical (observed) DLT rates at each dose level as responses and dose level sample sizes as weights, along with the pool adjacent violators algorithm (PAVA) to estimate the DLT rate at each dose level. Given the DLT estimates for each dose level, the MTD will be selected from all tried dose levels that have not been previously declared to be unsafe with a decision according to the mTPI decision table. With this

constraint, the MTD will be determined as the dose level with the DLT estimate closest to the target toxicity level of 30%.

Amendment 7

**Protocol Title: A Phase 1b Study Evaluating the Safety, Tolerability,
Pharmacokinetics and Efficacy of Delta-like Protein 3 Half-life Extended Bispecific
T-cell Engager AMG 757 in Subjects with De Novo or Treatment Emergent
Neuroendocrine Prostate Cancer**

Amgen Protocol Number Tarlatamab (AMG 757) 20200040

EU CT Number 2024-513316-10

NCT Number NCT04702737

Amendment Date: 21 June 2024

Rationale:

This protocol has primarily been amended to include the following changes:

- Update details about Protocol Approver and Key Sponsor Contact
- Remove EudraCT Number from the title page of the protocol.
- Align the protocol with the latest clinical protocol template.
- Remove 2 and 3 step dosing of cycle 1 scheduling tables (i.e. Table 1-1), Schedule of Activities tables (i.e. Table 1-3, Table 1-4), overall design Section 4.1 and step dosing Section 6.2.1.2.1.
- Update footnote e and ff for SoA table.
- Update Safety Follow-Up visit from 42 (\pm 5) days to 60 (+5) days.
- Remove Section 2.3.1.4 and Section 6.8.1 sucrose medicated renal impairment.
- Update provision of investigational product in Section 4.4.1
- Update male subjects use of contraception, use of condom and donating sperm timing from 132 days after the last dose of tarlatamab to 60 day after the last dose of tarlatamab.
- Update the title and content of Noninvestigational Products/Auxiliary Medicinal Products Section to be in accordance with European Union Clinical Trials

Regulation (EU CTR) and modify the wording “protocol-required therapy” to “noninvestigational product(s)/auxiliary medicinal product(s)”

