UPM	Unit probability mass
WHO	World health organization

Date: 24 March 2023 Page 12 of 53

1. Introduction

The purpose of this Statistical Analysis Plan (SAP) is to provide details of the statistical analyses that have been outlined within the protocol amendment 6 for study 20200040, **Tarlatamab (AMG 757)** dated 29 September 2022. The scope of this plan includes the interim analyses, the primary analysis and the final analysis that are planned and will be executed by the Amgen Global Biostatistical Science department unless otherwise specified.

2. Objectives, Endpoints/Estimands and Hypotheses

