For subjects who discontinued treatment for any reason other than progressive disease, every effort should be made to perform radiographic imaging (CT/MRI/bone scintigraphy) of the chest, abdomen, pelvis, bone, and all other known sites of disease every 3 months until documentation of disease progression per PCWG3 guidelines, clinical progression, start of new anticancer therapy, or up to 3 years after the last dose of tarlatamab, whichever occurs first.

Treatment-related serious adverse events and fatal serious adverse events regardless of the cause should be collected during long-term follow-up.

Percent Change from Baseline

Percent change from baseline is calculated using the following formula:

Percent change from baseline = [(post-baseline value - baseline value) / baseline

value] x 100

Relative Dose Intensity

Relative dose intensity is calculated using the following formula:

Relative dose intensity (%) = (Actual cumulative dose / Planned cumulative dose) x 100; where actual cumulative dose = sum of received doses, planned cumulative dose = planned dose accumulated over the actual treatment duration, i.e., 100 mg x (number of records in exposure dataset - 1) + 1 mg. Actual and planned cumulative dose up to the study visit are considered.

Safety Follow-up (SFU)

Upon permanent discontinuation from the study treatment for any reason to further assess the risk of delayed adverse events, a SFU visit will be performed approximately 42 (+ 5) days after the end of the last dose of tarlatamab.

Date: 24 March 2023 Page 20 of 53

Study Day

If the date is after the date of study day 1, then study day is calculated as following:

Study day = (date - date of study day 1) + 1

If the date is before the date of study day 1, then study day is calculated as following:

Study day = (date – date of **s**tudy **d**ay 1)

Study Day 1

Study Day 1 is defined as the date of the first dose of tarlatamab administration to the subject.

Treatment Duration

Treatment duration is calculated using the following formula:

Treatment duration (weeks) = (last dose **date** – first dose **date** + 1) / 7.

5.2 Primary Endpoint-related Definitions

Dose-Limiting Toxicity (DLT)

DLT is defined as any qualifying toxicity that is at least possibly related to tarlatamab with an onset within the first 28 days following first dose with either of the following criteria:

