- Grade 3 adverse event lasting more than 3 days (with the exception of fatigue and grade 3 non-febrile neutropenia that improves to ≤ grade 1 within 3 weeks including the use of growth factor support per neutropenia management guidelines [protocol Section 6.8.6]);
- ≥ Grade 4 adverse event regardless of duration (with the exception of grade 4 non-febrile neutropenia lasting less than or equal to 7 days including the use of growth factor support per neutropenia management guidelines [protocol Section 6.8.6]).
- Grade 5 adverse event

Laboratory parameters of Grade 3 or 4 of any duration, not considered clinically relevant, will not be considered DLTs.

Grade 4 electrolyte abnormalities that last < 72 hours, are not clinically complicated, and resolve spontaneously or respond to conventional medical interventions will not be considered DLTs.

Date: 24 March 2023 Page 21 of 53

The following adverse events will NOT be adjudicated as DLT regardless of the grade or duration:

- Lymphopenia
- Fever
- Tumor lysis syndrome (TLS) including associated manifestations attributable to TLS (e.g., electrolyte abnormalities, renal dysfunction, hyperuricemia)

DLT Evaluable

The DLT endpoint is evaluable if either: 1) the subject experiences a DLT, or 2) the subject does not experience a DLT and receives IP as planned in cycle 1 and has been followed for safety events a minimum of 28 days from start of treatment.

Maximum Tolerated Dose (MTD)

The MTD will be selected from all tried dose levels that have not been previously declared to be unsafe with a decision according to the mTPI decision table. The MTD will be estimated using isotonic regression (Ji et al, 2010) and the MTD will be the dose level with the estimated DLT rate closest to 0.30.

Treatment-Emergent Adverse Event (TEAE)

TEAE is defined as adverse events starting on or after first dose of tarlatamab as determined by "Did event start before first dose of investigational product" equal to "No" or missing on the Events CRF, and up to and including 47 days after the last dose of tarlatamab excluding the events reported after End of Study date.

Treatment-related Adverse Event (TRAE)

TRAE is defined as treatment-emergent AE that per investigator review has a reasonable possibility of being caused by **tarlatamab** as indicated on the Events CRF page.

5.3 Secondary Endpoint-related Definitions

Best Overall Response (BOR) per RECIST 1.1

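### The SAP supplied ends its TEAE and TRAE window 47 days after the last dose, while the current protocol follows subjects for adverse events to a visit at 60 (+5) days

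*SAP*

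**What the plan says.** SAP section 5.2 (Primary Endpoint-related Definitions) starts the TEAE window at the first dose and closes it "up to and including 47 days after the last dose of tarlatamab excluding the events reported after End of Study date". The same section defines a TRAE as a treatment-emergent event that the investigator considers possibly caused by tarlatamab.

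SAP section 5.1 (General Definitions) says that "a SFU visit will be performed approximately 42 (+ 5) days after the end of the last dose of tarlatamab". SAP section 1 states that the plan details the analyses "outlined within the protocol amendment 6 for study 20200040".

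The current protocol is Amendment 7 ("Amendment Date: 21 June 2024"). Its synopsis says that "the subject must return for safety follow-up (SFU) visit approximately 60 (+5) days after the last dose of tarlatamab", and sections 1.2, 4.4.2 and 8.1.3 and the Schedule of Activities footnotes agree. Protocol sections 8.2.4.1.1 and 8.2.4.1.2 collect adverse events and serious adverse events to the later of that visit and a limit of 60 days counted from the end of the dosing interval.

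Protocol Appendix 4 (section 11.4) leaves the TEAE definition to the SAP. Protocol section 9.4 requires the SAP to be final before database lock.

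**The concern.** TEAEs and TRAEs are primary endpoints (protocol section 3). The synopsis gives the purpose of the safety follow-up visit as assessing the risk of delayed adverse events. If the SAP supplied is applied to data collected under the current protocol, events that start late in the follow-up period are recorded but are not TEAEs by definition. They then drop out of the TEAE and TRAE tables in SAP sections 9.6.1 and 9.6.2, including those for serious, grade 3 or above, and fatal events. The protocol has no TEAE window of its own, so nothing in it corrects the SAP's limit.

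**Working it through.** All days are counted from the last dose of tarlatamab.

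**Inputs**
- TEAE window end: day 47 (SAP 5.2)
- SAP safety follow-up visit: day 42, tolerance +5 (SAP 5.1)
- Current safety follow-up visit: day 60, tolerance +5 (protocol 1.1, 4.4.2, 8.1.3)
- Dates: SAP 24 March 2023; Amendment 7 21 June 2024

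**Step 1. Reproduce the SAP's figure.** Visit day plus tolerance: 42 + 5 = 47. The match is exact, so the window was consistent with the visit schedule when the SAP was written.

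**Step 2. Order of the documents.** From 24 March 2023 to 21 June 2024 is 366 + 89 = 455 days. The SAP supplied predates Amendment 7.

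**Step 3. Gap to the current visit.** An on-time visit falls on day 60 to 65.
- Shortest gap: 60 − 47 = 13 days
- Longest gap: 65 − 47 = 18 days

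**Step 4. Which events are excluded.** SAP 5.2 classifies by start date. An event found on day 60 that began on day 45 is a TEAE. An event that began on day 50 is not, even though the protocol collects it.

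**Step 5. Same convention, current schedule.** Visit day plus tolerance: 60 + 5 = 65.

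**Step 6. Scale.** SAP 9.1 splits analyses by part and by Part 2 group, and the planned final size is 40 per group. In a full group of 40, each subject whose only occurrence of a term starts after day 47 lowers that term's incidence by 1/40 = 2.5 percentage points. This is a unit of measure, not an estimated effect. The documents give neither the number of subjects followed under Amendment 7 nor an event rate after day 47.

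**The case against.** The strongest reply is that nothing was wrong when the SAP was written. It states which amendment it covers and is consistent with the visit schedule it describes. It need only be final before database lock, so a later version may exist. That stands: the documents show that the SAP supplied predates Amendment 7, not that the sponsor failed to update it.

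A second reply is that a TEAE window need not match the collection period, and that a common day-47 cut-off treats all subjects alike, because those who finished under the 42-day visit cannot be followed further. This has merit and is why the day-47 table should be kept. It does not explain why the main tables should stop at the old visit limit, and the SAP gives no reason for doing so.

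Third, the effect may be small. The limit does not bind for subjects still on treatment or within 47 days of their last dose at a data cut-off. Protocol 8.1.3 restricts its list of visit procedures: "The following procedures will be completed for patients who have not started subsequent anti-cancer therapy". Related serious events are still reported to the sponsor (protocol 8.2.4.1.3), and SAP 5.1 says that related serious events and fatal serious events should be collected in long-term follow-up. These points limit the loss, but reporting an event is not the same as tabulating it, and no visible table is specified to include these events. One SAP subsection, between 9.6.6 and 9.6.8, is not visible, and the events-of-interest summary in 9.6.2 states no window.

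Three stronger readings are tempting and are not supported:
- *Everything found at the visit is lost.* Exclusion is by onset, so only events that start on day 48 or later are affected.
- *The gap runs to the end of the collection period.* That limit lies beyond day 65, but its exact day depends on the last day of the dosing interval, which the protocol does not define. No passage requires the TEAE window to reach it. The SAP's own convention is visit plus tolerance, so the relevant gap is 13 to 18 days.
- *The expansion stopping rule is compromised.* SAP 7.1 uses the rate of grade 4 or higher treatment-related events, and SAP 5.2 defines TRAE, so the window carries over to that rule. The documents show no lost event and no altered decision. The dose level review team sees all available data.

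**Conclusion.** The mismatch is real and rests on the current text of both documents. Applied together as written, they leave collected adverse events with onset from day 48 to the safety follow-up visit (13 to 18 days) out of the TEAE and TRAE tables. This holds for subjects followed under Amendment 7 and assumes an on-time visit. It also assumes that the SAP supplied is the one applied; if a later version exists, the sponsor need only confirm that it changed the definition. The number of events left out cannot be derived and could be zero. The DLT, laboratory, vital-sign and efficacy analyses do not use this window. The change is worth making because it concerns a primary endpoint, costs little, and can be made only in the SAP.

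**What to change.** Before database lock, update the SAP to Amendment 7:

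1. In section 5.1, change the safety follow-up visit to 60 (+5) days.
2. In section 5.2, end the TEAE window at day 65 inclusive after the last dose (visit day plus tolerance, as now) and keep the existing End of Study exclusion. TRAE inherits the new limit.
3. Keep the day-47 tabulation of TEAEs and TRAEs for all subjects as a sensitivity table, and state how many subjects were followed under each visit schedule.
4. List collected adverse events with onset after day 65, including related and fatal serious events from long-term follow-up.

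The cost is two changed definitions, one derivation, one extra table and one listing. No new data are needed. The day-65 table will mix two follow-up lengths, because subjects who finished under the 42-day visit cannot be extended; the day-47 table gives the like-for-like comparison. Reported incidences may rise slightly, and some of the added events may reflect progression or subsequent therapy.
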